### **9.3 Baseline Documentation of Target and Non-Target Lesions**

#### **9.3.1 Target Lesions:**

When more than one measurable lesion is present at baseline all lesions up to a maximum of five lesions total (and a maximum of two lesions per organ) representative of all involved organs should be identified as target lesions and will be recorded and measured at baseline (this means in instances where patients have only one or two organ sites involved a maximum of two and four lesions respectively will be recorded).

#### **9.3.2 Lymph Nodes:**

These merit special mention since they are normal anatomical structures which may be visible by imaging even if not involved by tumor. Pathological nodes which are defined as measurable and may be identified as target lesions must meet the criterion of a short axis of  $\geq 15$  mm by CT scan. Only the short axis of these nodes will contribute to the baseline sum. The short axis of the node is the diameter normally used by radiologists to judge if a node is involved by solid tumor. Nodal size is normally reported as two dimensions in the plane in which the image is obtained (for CT scan this is almost always the axial plane; for MRI the plane of acquisition may be axial, sagittal or coronal). The smaller of these measures is the short axis. All other pathological nodes (those with short axis  $\geq 10$  mm but  $< 15$  mm) should be considered non-target lesions. Nodes that have a short axis  $< 10$  mm are considered non-pathological and should not be recorded or followed.

A sum of the diameters (longest for non-nodal lesions, short axis for nodal lesions) for all target lesions will be calculated and reported as the baseline sum diameters. If lymph nodes are to be included in the sum, then as noted above, only the short axis is added into the sum. The baseline sum diameters will be used as reference to further characterize any objective tumor regression in the measurable dimension of the disease.

#### **9.3.3 Non-Target Lesions:**

All non-measurable lesions (or sites of disease) plus any measurable lesions over and above the 5 listed as *target lesions*. Measurements are not required but these lesions should be noted at baseline and should be followed as "present" or "absent."

### **9.4 Evaluation of Best Overall Response**

In general, the patient's best response assignment will depend on the achievement of both measurement and confirmation criteria as outlined below and summarized in Table 1:

*Complete Response (CR):* Disappearance of all target lesions. Any pathological lymph nodes (whether target or non-target) must have reduction in short axis to  $< 10$  mm.

*Partial Response (PR):* At least a 30% decrease in the sum of diameters of target lesions, taking as reference the baseline sum diameters.

**Progressive Disease (PD):** At least a 20% increase in the sum of diameters of target lesions, taking as reference the smallest sum on study (this includes the baseline sum if that is the smallest on study). In addition to the relative increase of 20%, the sum must also demonstrate an absolute increase of at least 5 mm. (Note: the appearance of one or more new lesions is also considered progression).

**Stable Disease (SD):** Neither sufficient shrinkage to qualify for PR nor sufficient increase to qualify for PD, taking as reference the smallest sum of diameters while on study.

Table 1: Response Assessment in Patients with Measurable Disease

TARGET LESIONS	NON-TARGET LESIONS	NEW LESIONS	OVERALL RESPONSE	BEST RESPONSE FOR THIS CATEGORY ALSO REQUIRES:
CR	CR	No	CR	≥4 weeks confirmation
CR PR	Non-CR/Non-PD	No	PR	≥4 weeks confirmation
	Non-PD	No	PR	
SD	Non-PD	No	SD	Documented at least once >6 wks from baseline
PD	Any	Yes or No	PD	
Any	PD	Yes or No	PD	No prior SD, PR, or CR
Any	Any	Yes	PD	

CR=complete response, PR=partial response, PD=progressive disease, SD=stable disease

Every effort should be made to document the objective progression even after discontinuation of treatment

Response duration will be measured from the time measurement criteria for CR/PR (whichever is first recorded) are first met until the first date that recurrent or PD is objectively documented.

Stable disease duration will be measured from the time of start of therapy until the criteria for progression are met, taking as reference the smallest measurements recorded since the treatment started.

## 9.5 Evaluation of Response for Non-Measurable Disease

When the patient has only non-measurable disease, the same general concepts apply here as noted above. However, in this instance there is no measurable disease assessment to factor into the interpretation of an increase in non-measurable disease burden. Because worsening in non-target disease cannot be easily quantified (by definition: if all lesions are truly non-measurable) a useful test that can be applied when assessing patients for unequivocal progression is to consider if the increase in overall disease burden based on the change in non-measurable disease is comparable in magnitude to the increase that would be required to declare PD for measurable disease: i.e. an increase in tumor burden representing an additional 73% increase in 'volume' (which is equivalent to a 20% increase diameter in a measurable lesion). Examples include an increase in a pleural effusion from 'trace' to 'large', an increase in lymphangitic disease from localized to widespread, or may be described in

protocols as 'sufficient to require a change in therapy'. If 'unequivocal progression' is seen, the patient should be considered to have had overall PD at that point. While it would be ideal to have objective criteria to apply to non-measurable disease, the very nature of that disease makes it impossible to do so, therefore the increase must be substantial.

It is assumed that at each protocol specified time point, a response assessment occurs. When patients have non-measurable (therefore non-target) disease only, Table 2 is to be used.

Table 2: Response Assessment in Patients with Non-Measurable (Non-Target) Disease

NON-TARGET LESIONS	NEW LESIONS	OVERALL RESPONSE
CR	No	CR
Non-CR/Non-PD	No	Non-CR/Non-PD
Not all evaluated	No	NE
Unequivocal PD	Yes or No	PD
Any	Yes	PD

*CR=complete response, PD=progressive disease, NE=inevaluable*

## 10. SUBJECT DISCONTINUATION

Patients will receive 8 cycles of neoadjuvant mFOLFIRINOX followed by SBRT, surgical resection, and post-operative mFOLFIRINOX to complete 12 cycles. Treatment will continue unless there is evidence of disease progression, or unacceptable toxicity as specified in section 7.3 of the protocol. Any patients deemed unresectable at the time of surgery will be discontinued from study treatment.

Patients who complete the study treatment phase without disease progression will enter a post-study surveillance phase. They will undergo history, physical exam, measurement of weight, evaluation of performance status, and laboratory assessments (including CBC, serum chemistries, liver function tests, CA 19-9, CEA, and a research blood collection, as specified in the study calendar) at three month intervals for three years, then every six months for two years, then annually or until disease recurrence or death. Cross-sectional imaging with CT or MRI will be performed at 6 month intervals for three years, and then annually for two additional years or until disease recurrence. After five years, patients will be followed annually until death; surveillance imaging and lab assessments are optional after five years.

In addition, subjects who meet the following criteria should be discontinued from study treatment:

- Any grade 3 or 4 toxicity that does not resolve within 3 weeks of holding treatment.
- Unwillingness or inability of subject to comply with study requirements
- Determination by the investigator that it is no longer safe for the subject to continue therapy, or that the constraints of this protocol are detrimental to the patient's health
- The patient no longer wishes to continue protocol therapy

All subjects will be followed for survival.

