### 2.2 Secondary Objectives

- 2.2.1 To evaluate the radiographic response to neoadjuvant therapy by comparing IV contrast CT scans before and after therapy.
- 2.2.2 To evaluate the pathologic response to neoadjuvant chemotherapy and stereotactic radiation.
- 2.2.3 To determine rates of recurrence (local only, systemic only, and both local and systemic), progression free survival, and overall survival.
- 2.2.4 To determine rates of grade 3 or greater gastrointestinal toxicity, including acute toxicities occurring within 3 months of treatment, and late toxicities occurring over 3 months after completion of radiation.

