receive 4 additional cycles of mFOLFIRINOX to complete a total of 12 cycles, with further dose modifications at the discretion of the treating medical oncologist.

Patients who complete the study treatment without disease progression will then enter a period of post-study surveillance which will include a history, physical exam, and laboratory assessments at three month intervals for three years and then 6 month intervals for two years, and CT scans at 6 month intervals for a total of three years, and then annually for an additional two years. After five years, patients will be followed annually until death.

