Surgical Resection M					

Long Term Follow-up PeriodN:			
Tests & Observations	Every 3 months (for the first three years after completing mFOLFIRINOX)	Every 6 months (three years after completing mFOLFIRINOX for the next two years)	Annual (five years after completing mFOLFIRINOX)
Scheduling Window (Days)	Every 3 months ±14 days	Every 6 months ±14 days	Annually ± 14 days
History	x	x	x
Physical Exam	x	x	x
Weight/BSA	x	x	x
Performance Status	x	x	x
Laboratory StudiesA:			
CBC, Diff, Platelets	x	x	x
Serum Chemistries B	x	x	x
CA 19-9, CEA	x	x	x
Research Blood Collection E	x	x	x

Follow-up PeriodN:		
Staging:	Every 6 months (first three years after completing mFOLFIRINOX)	Annually (three years after completing mFOLFIRINOX for two years)
Scheduling Window (Days)	Every 6 months ±14 days	Annually ±14 days
CT (or MRI) F	x	x

- A** Laboratory studies must be drawn within 24 hours of administration of drugs
- B** Serum chemistry panel will include serum creatinine, BUN, electrolytes (Na, K, Cl, Bicarb), AST/ALT, Alk Phos, Bili, and albumin
- C** PT/INR should be monitored weekly for those taking coumadin or warfarin
- D** For women of child-bearing potential only
- E** 3 purple top tubes (30 mls) at diagnosis, and 2 – 3 purple top tubes (20 – 30 mls) at each follow up time point, for cryopreservation of plasma and buffy coat
- F** CT should be performed using pancreatic protocol when possible. For patients who are unable to undergo CT, MRI may be used
- G** If elastography is not feasible, patients can remain on study
- H** At the time of diagnosis, core biopsies will be attempted with one specimen sent to pathology for diagnosis and a separate specimen to be banked for correlative studies. If core biopsies are not successful, a FNA is acceptable for diagnosis. At the time of EUS for fiducial placement, a core biopsy will be obtained and banked for correlative studies. Patients can continue on study if core biopsy is not feasible at the time of fiducial placement.
- I** At the time of CT simulation
- J** On the day of fraction 3 and fraction 5 of SBRT
- K** CT scan and plasma and serum samples will be done within 4 weeks prior to surgery
- L** Endoscopic ultrasound is optional if deemed necessary for surgical assessment

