### **13. ADVERSE EVENTS ANALYSIS, DEFINITION, AND REPORTING**

#### **13.1 Safety Analysis**

Safety will be analyzed for patients treated in this study.

At each visit, a brief focused history will be obtained and any indication of treatment related toxicity will be evaluated by appropriate examination and/or laboratory/radiographic studies.

Safety analyses will include summaries of adverse event rates and changes in laboratory results, as well as number of CTCAE toxicity grades for both laboratory and non-laboratory data.

The evaluation period should extend from date of first treatment until at least 30 days (or longer if so specified) from the last dose or until resolution from all acute toxicities associated with the drug administration.

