### **14.2 Duration of Reporting of SAEs**

From the date of first treatment until 30 days (unless otherwise specified) subsequent to last treatment or withdrawal of subject, new onset adverse events will be captured. Follow-up and reporting of these events will follow the same procedure as for AEs observed during the study period. In addition, any unexpected Serious Adverse Event that occurs more than 30 days after drug administration but is possibly, probably or definitely attributed to drug administration will be recorded and reported.

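### SBRT recipients who are not resected, or who leave before adjuvant therapy, have no scheduled toxicity assessment in the late window, so the late GI toxicity rate would come mainly from completers

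*Combined protocol and SAP*

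**What the plan says.** Objective 2.2.4 and outcome 3.3.2.6 ask for the rate of grade 3 or higher GI toxicity, acute and late. Late events are "late toxicities occurring over 3 months after completion of radiation", with no upper limit.

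Who is seen after treatment is set in two places. Section 3.1: "Patients who complete the study treatment without disease progression will then enter a period of post-study surveillance". Section 10: "Patients who complete the study treatment phase without disease progression will enter a post-study surveillance phase". Section 10 also says "Any patients deemed unresectable at the time of surgery will be discontinued from study treatment". The only follow-up promised to everyone is this: "All subjects will be followed for survival". No frequency or method is given for it.

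Section 14.2 captures new adverse events from first treatment "until 30 days (unless otherwise specified) subsequent to last treatment or withdrawal of subject". After that it asks only for unexpected serious events attributed to drug administration. Section 13.1 says "Safety will be analyzed for patients treated in this study" and calls for a toxicity-directed history at each visit. Section 12 lists the late rate as a secondary endpoint but gives no denominator, time horizon or handling of death.

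The Section 8 calendar marks a toxicity assessment on day 1 of neoadjuvant cycles, weekly during SBRT and on day 1 of adjuvant cycles. None is marked in post-treatment or long-term follow-up. The long-term columns count from the end of chemotherapy ("Every 3 months (for the first three years after completing mFOLFIRINOX"), so a patient who never finishes it has no start date for them.

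**The concern.** Everyone who receives SBRT is at risk of late injury, but the plan schedules late contact by treatment completion. A patient found unresectable after SBRT, or who progresses or stops before adjuvant therapy, has had the full radiation exposure and then has no scheduled occasion on which a late GI event would be asked about.

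Two things can follow. If the denominator is all treated patients, as Section 13.1 suggests, unobserved patients count as free of late toxicity and the rate is understated. If they are left out, the rate describes a selected group: resected patients who reached adjuvant therapy, most of whom finished it without progression. Late GI toxicity is a prominent reported harm of SBRT in the protocol's own background (Section 1.5), so a reader would want this rate for all who were irradiated.

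**Working it through.** The plan states no figure for the late rate, its denominator or its precision, so there is nothing to reproduce. The check has two parts: when capture ends, and how many patients and events may be involved.

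**1. Timing, in days after the end of SBRT.** The late window opens at 3 × 30.4 = day 91 (week 13.0). Section 14.2 adds 30 days (4.3 weeks) to the last treatment or withdrawal. Surgery is at 4 to 12 weeks, days 28 to 84 (Section 6.3). Adjuvant therapy starts up to 12 weeks after surgery, in 2-week cycles (Sections 6.1, 6.4). Section 14.2 is read generously here: an operation counts as treatment and discontinuation counts as withdrawal.

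| Patient | Capture ends | Late days covered |
|---|---|---|
| SBRT is the last treatment | 30 | 0 |
| Operation or discontinuation on day 28, nothing after | 28 + 30 = 58 | 0 |
| Same, day 61 | 61 + 30 = 91 | 0 |
| Same, day 84 | 84 + 30 = 114 | 114 − 91 = 23 |
| Operation day 84, adjuvant from day 168, stopped after cycle 3 (given day 196) | 196 + 30 = 226 | 226 − 91 = 135 |

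When SBRT is the last treatment, capture ends 91 − 30 = 61 days, about 9 weeks, before the window opens. The last row shows that a resected patient who starts adjuvant therapy can be well covered without completing it.

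**2. Number of unresected SBRT recipients.** Assumptions, for full enrolment of 28:
- S, the number receiving SBRT, is 20 to 28. The protocol gives no figure.
- The share of all 28 who are resected is 41% (the gemcitabine series in Section 12) to 68% (the mFOLFIRINOX and chemoradiation trial in Section 1.3). So R = 0.41 × 28 ≈ 11 to 0.68 × 28 ≈ 19.
- All resected patients have had SBRT.
- The late grade 3 or higher rate is the 8% cited in Section 4.3, equal in all SBRT recipients.

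Unresected recipients are U = S − R and their expected late events are 0.08 × U. If they count as event-free and resected patients are fully observed, the rate over SBRT recipients reads 8% × R/S.

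| S | R | U | Events at risk of being missed | Rate read instead of 8% |
|---|---|---|---|---|
| 20 | 19 | 1 | 0.08 | 7.6% |
| 28 | 19 | 9 | 0.72 | 5.4% |
| 20 | 11 | 9 | 0.72 | 4.4% |
| 28 | 11 | 17 | 1.36 | 3.1% |

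Total expected late events are 0.08 × 20 = 1.6 to 0.08 × 28 = 2.24. If unresected patients have half the 8% rate, the missed events run from 0.04 × 1 = 0.04 to 0.04 × 17 = 0.68. At twice the rate they run from 0.16 × 1 = 0.16 to 0.16 × 17 = 2.72. Resected patients who leave before adjuvant therapy would add to U; the documents give no basis for counting them.

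**3. Are unresected patients alive in the late window?** The SBRT study in locally advanced disease using this dose had a median survival of 13.9 months (Section 1.5). Assume exponential survival from the start of treatment, and a late window opening at about month 8 (roughly 4 months of chemotherapy, 1 for SBRT and 3 afterwards). Then exp(−ln 2 × 8/13.9) = 0.67, so about two thirds would be alive.

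**The case against.** The strongest reply is that the plan sees more non-completers than Section 10 alone suggests. After surgery, patients are seen every 2 weeks in medical oncology (Section 6.4), with a toxicity assessment on day 1 of each adjuvant cycle. These can fall in the late window for someone who later stops or progresses. That stands. A reader might infer that the late rate rests on completers alone, that everyone else is followed for nothing but survival, or that a non-completer can have no more than 23 days of late capture. The documents support none of these. Section 6.3 also allows operations beyond 12 weeks with approval, so 23 days is not a ceiling even for patients who never start adjuvant therapy.

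Other clauses show contact with unresected patients. The interim review in Section 4.3 needs 3 months of follow-up after SBRT in 5 patients, but it ends where the late window begins. Sections 6.2 and 7.4.3 require acid suppression for at least 6 months after SBRT in patients without surgery, which implies continuing care but no toxicity recording. Section 9.4 asks for progression to be documented after treatment stops and says nothing about toxicity. Sections 13.1 and 14.2 allow a longer capture period where one is specified. Objective 2.2.4 might be read as specifying it, but no section then provides a visit or contact for unresected patients.

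It is also fair that the endpoint is descriptive, that Section 12 disclaims power for it, and that the expected number of missed events is small.

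**Conclusion.** The gap is real but limited. SBRT recipients who are not resected, or who progress or stop before adjuvant therapy, have no scheduled toxicity assessment in the late window. The late rate would come mainly from completers, plus resected patients seen during adjuvant cycles. Even for completers the long-term calendar has no toxicity row; their coverage depends on the general instruction in Section 13.1, and note N allows visits to stop at recurrence.

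The size is uncertain: about 1 to 17 unresected SBRT recipients and roughly 0.1 to 1.4 unrecorded late events. This rests on the assumed 20 to 28 SBRT recipients, the 41% to 68% resection range, and an equal 8% rate. A reader might be tempted to narrow the range by applying a published unresected share directly to SBRT recipients. The 68% in Section 1.3 is a share of all patients in that trial, so those lost before radiation are already among its unresected. A reader might also cite the 26.6-month median from the institution's locally advanced series as survival without resection. Section 1.4 reports that 13 of those 31 patients had R0 resections, so it is not an unresected population.

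The primary endpoint and the stopping rules are unaffected. This is a cheap improvement to a secondary safety rate.

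**What to change.** - **Sections 10 and 14.2:** state that, for every patient who receives at least one SBRT fraction, grade 3 or higher GI toxicity is recorded about every 3 months by phone or chart review, until death or for a fixed period (for example 12 to 24 months), regardless of resection, progression or stopping treatment.
- **Section 8:** add a toxicity row to the long-term calendar.
- **Section 12:** report the late rate over SBRT recipients, either with length of follow-up given or as cumulative incidence with death as a competing event.

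Cost: a few sentences, one calendar row and a light contact schedule for a small number of patients. Survival follow-up has no stated timetable, so the contacts cannot be assumed to exist already. No new clinic visit, procedure or staff is needed. The reported late rate may rise.

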## 11. STUDY DISCONTINUATION

The Principal Investigator has the right to terminate this study at any time if the incidence or severity of adverse events in this or other studies indicates a potential health hazard to subjects.

## 12. STATISTICAL METHODS

The primary endpoint of this phase II study is the R0 resection rate after neoadjuvant mFOLFIRINOX and SBRT in patients with BRPC.

In the largest reported series of patients with BRPC, 125 patients received pre-operative therapy consisting of 2 to 4 months of gemcitabine-based chemotherapy followed by fractionated chemoradiation. 41% of patients underwent a subsequent resection, and R0 resections were achieved in 94% of these patients, for an overall R0 resection rate of 39% for all patients initiating pre-operative therapy. Superior outcomes have been demonstrated with FOLFIRINOX compared to gemcitabine chemotherapy, and a local control benefit has been suggested with SBRT compared to fractionated chemoradiation. Thus, we propose an increase in the R0 resection rate from 40% in historical controls treated with standard gemcitabine-based chemotherapy and fractionated radiation prior to surgery to 65% with pre-operative FOLFIRINOX and SBRT.

A total of 28 patients will be enrolled in a Simon two-stage design with a provision for early stopping for lack of efficacy. The primary endpoint is the rate of achieving R0 resections. Patients needing to drop out of this study prior to surgery, for disease progression or treatment related toxicity, will be considered as failing to achieve the R0 resection rate. The null hypothesis is this rate is 40% based on both reported historical rates as well as our experience at Yale-New Haven Hospital. Under the alternative hypothesis, we will judge pre-operative modified FOLFIRINOX followed by SBRT effective if the R0 resection rate is 65% or higher. The optimal Simon two-stage design will terminate early if 5 or fewer of the first 13 patients fail to achieve an R0 resection. Otherwise we continue and enroll the remaining 15 patients for a total of 28. If 15 or more out of the full 28 achieve R0 resection then we reject the null hypothesis. This design has 90% power and significance level 0.1. The probability of stopping early under the null hypothesis is 57%.

Secondary endpoints include radiographic response to neoadjuvant therapy, pathologic response to neoadjuvant therapy, rates of recurrence (local only, systemic only, and both local and systemic), progression free survival, overall survival, and rates of grade 3 or greater acute and late gastrointestinal toxicity. We will compare levels of KRAS mutation-associated circulating tumor DNA, CA19-9, and elastography measures with outcomes including R0 resection using logistic regression, and progression free survival and overall survival using proportional hazards regression. We will code IV contrast scans as binary and compare the before/after treatment within the same subject using the McNemar test for matched pairs. We have not powered this study for these secondary and exploratory measures. Future correlative biomarker studies will be studied using standard bioinformatics methods. Progression free survival, and overall survival will be estimated using Kaplan-Meier analysis. The Cox proportional hazards regression model will be used to determine if survival outcomes are associated with patient characteristics or treatment-related toxicities.

We anticipate accrual will be completed in two years based on the fact that approximately 40 resections for pancreatic adenocarcinoma are performed annually at Yale New Haven Hospital, of which around a third are for BRPC.

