### **3.4 Expected Accrual**

We expect to accrue 28 patients over approximately 56 months. Approximately 40 resections for pancreatic adenocarcinoma are performed annually at Yale New Haven Hospital, of which approximately one third are for BRPC. Therefore we anticipate enrolling approximately 6 patients per year.

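### The stage-1 futility rule is inverted: as printed, it stops the trial when 8 or more of the first 13 patients achieve R0 and continues when few do

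*Combined protocol and SAP*

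**What the plan says.** Section 12 sets out a Simon two-stage design with 28 patients, 13 in stage 1 and 15 in stage 2. The null R0 resection rate is 40% and the alternative is 65%. The interim look is described as a design "with a provision for early stopping for lack of efficacy". The operative rule is: "The optimal Simon two-stage design will terminate early if 5 or fewer of the first 13 patients fail to achieve an R0 resection".

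The rest of the paragraph gives the final criterion and the operating characteristics:

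- The final analysis rejects the null at 15 or more R0 resections out of 28.
- On error rates, the plan states: "This design has 90% power and significance level 0.1".
- For the chance of ending at stage 1 when the true rate is 40%, it says: "The probability of stopping early under the null hypothesis is 57" (per cent).

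It also says how patients who leave before surgery because of progression or treatment-related toxicity are counted: they "will be considered as failing to achieve the R0 resection rate".

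The stage-1 boundary appears nowhere else in the document. Section 4.3 (toxicity look after 5 patients), Section 11 (termination for adverse events) and Section 15 (safety review by the monitoring committee after 10 patients) deal with safety only.

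**The concern.** With 13 patients, failures and R0 resections sum to 13, so a limit of at most 5 failures is the same as at least 8 R0 resections. Read literally, the rule stops the trial when 8 to 13 patients have had an R0 resection and carries on when 0 to 7 have. That is the reverse of a futility stop.

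The counting of early drop-outs makes this worse. A patient lost to progression or toxicity is a failure, so under the printed rule each such loss pushes the failure count above 5 and helps keep the trial open.

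This is the only stopping rule on the primary endpoint. Applied literally, it gives no protection against continuing an ineffective regimen. With no R0 resections in the first 13 patients it would still enrol 15 more, although all 15 would then have to succeed to reach 15 of 28. With 8 R0 resections in 13, the trial would close.

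**Working it through.** **Inputs (all from Section 12).** n1 = 13, n2 = 15, N = 28; p0 = 0.40, p1 = 0.65; reject the null at 15 or more R0 resections out of 28. Let X be the number of R0 resections in stage 1, X ~ Bin(13, p), and Y the number in stage 2, Y ~ Bin(15, p).

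**Step 1: reproduce the plan's figures, counting R0 resections.** Stop if X ≤ 5.

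- P(stop) = P(X ≤ 5 | 13, 0.40). The terms for X = 0 to 3 sum to 0.1686. Adding X = 4 gives 0.3530, and adding X = 5 gives **0.5744**, the stated 57%.
- P(reject) = Σ over x = 6 to 13 of P(X = x) · P(Y ≥ 15 − x). This is **0.0930** at p = 0.40 and **0.9035** at p = 0.65, against the stated 0.1 and 90%.
- P(stop) at p = 0.65 is 0.0462.
- Expected sample size = 13 + (1 − P(stop)) × 15. At 40% this is 13 + 0.4256 × 15 = 19.4; at 65% it is 13 + 0.9538 × 15 = 27.3.

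A grid search over two-stage designs with type I error at most 0.10 and power at least 0.90 returns this same design (stop at 5 of 13, reject at 15 of 28) as the one with the smallest expected sample size under the null. The plan's description of it as optimal is therefore correct.

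**Step 2: apply the rule as printed.** Stop if failures ≤ 5, that is, X ≥ 8.

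- At p = 0.40: P(X ≥ 8) = **0.0977**.
- At p = 0.65: P(X ≥ 8) = **0.7159**.
- Expected sample size at 40%: 13 + 0.9023 × 15 = 26.5. At 65%: 13 + 0.2841 × 15 = 17.3.
- If a stop means the null is not rejected, P(reject) = Σ over x = 0 to 7 of P(X = x) · P(Y ≥ 15 − x). This is 0.0561 at 40% and **0.2229** at 65%.

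| Quantity | Stated | Stop if ≤ 5 of 13 achieve R0 | Stop if ≤ 5 of 13 fail (as printed) |
|---|---|---|---|
| P(stop early), true rate 40% | 57% | 57.4% | 9.8% |
| P(stop early), true rate 65% | not given | 4.6% | 71.6% |
| Type I error (40%) | 0.1 | 0.093 | 0.056 |
| Power (65%) | 90% | 90.4% | 22.3% |
| Expected N, 40% | not given | 19.4 | 26.5 |
| Expected N, 65% | not given | 27.3 | 17.3 |

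**Step 3: can any other reading rescue the printed wording?**

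- Treating a literal stop as a declaration of success gives type I error 0.0977 + 0.0561 = 0.1538 and power 0.7159 + 0.2229 = 0.9388. The type I error exceeds 0.1, and the early-stopping probability is still 9.8%.
- Changing the number does not help. Failure cut-offs of 3, 4, 5, 6 and 7 out of 13 give null stopping probabilities of 0.8%, 3.2%, 9.8%, 22.9% and 42.6%. None is 57%.

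**Step 4: the extreme case.** With X = 0 the printed rule continues, and rejection then needs Y = 15. Even at p = 0.65 that has probability 0.65^15 = 0.0016.

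**The case against.** The best defence is that the intent can be recovered from the same paragraph. It names a Simon design, says the stop is for lack of efficacy, defines the endpoint as achieving R0, and gives a 57% null stopping probability. Only one rule fits all of that, and a statistician would probably see the sentence as a slip in which two phrasings were merged. The documents do not show that anyone would apply it literally, so the figures for the printed rule describe a possible harm, not an expected one.

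Two narrower points also have force. First, because the paragraph gives early stopping a single purpose, the natural reading of any stop is that the null is not rejected. The success reading in the working has no textual basis and is shown only for completeness. Second, under the non-rejection reading the type I error of 5.6% is within the 0.1 limit; what fails is the power and the 57%.

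All of this stands, but it does not make the sentence acceptable. The sentence is complete and grammatical, with no sign of damage or redaction, and nothing elsewhere corrects it. Whoever conducts the look would have to depart from the protocol's literal text, with interim results in hand, to do what was meant. A prespecified decision rule should not depend on that.

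**Conclusion.** The concern holds, and the sentence must be corrected. As printed, the stage-1 rule is the reverse of its stated purpose. It stops with probability 9.8% instead of 57% when the regimen is no better than the null, and 71.6% instead of 4.6% when the regimen is as good as hoped. With a stop taken as non-rejection, power is 22.3% instead of 90%.

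The error is confined to the wording. The sample size, both cut-offs and all stated operating characteristics are correct once R0 resections are counted. An exact type I error of 0.093 against a stated 0.1 is ordinary discreteness, not a discrepancy.

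These figures assume independent patients with a common R0 rate, exactly 13 and 15 patients evaluated at the two stages, and drop-outs before surgery for progression or toxicity counted as failures, as the plan specifies.

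**What to change.** Reword the stage-1 sentence in Section 12 along these lines: *The trial stops for lack of efficacy if at most 5 of the first 13 patients have an R0 resection; with 6 or more, a further 15 patients are enrolled.* The cost is a one-sentence amendment. Sample size, thresholds, error rates and the 57% stay as they are.

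Two small items could be tidied in the same amendment; neither bears on the verdict above.

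- Section 12 says the regimen will be judged effective at an R0 rate of 65% or more, but the null is rejected at 15 of 28, an observed rate of 15/28 = 53.6%. State that 65% is the rate assumed for power and that 15 of 28 is the success criterion.
- Section 12 says "We anticipate accrual will be completed in two years", whereas Section 3.4 says "We expect to accrue 28 patients over approximately 56 months". The latter matches its own rate of about 6 patients a year (28 / 6 = 4.67 years = 56 months). The two statements should be reconciled.
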